Specific Aim. Our aim is to compare the effectiveness of achieving weight loss between two Diabetes Prevention Program Lifestyle Interventions (DPP-LI), the WORD DPP-LI¹⁸⁻²⁰ and a culturally-adapted PILI DPP-LI²¹⁻²², in the Marshallese population using a randomized controlled trial (RCT) with a goal of 378 participants.

Study design. The study design is a comparative effectiveness research (CER), RCT conducted in church settings or other community setting convenient to the participant group with the Marshallese population. Churches were selected as the primary setting based on stakeholder input.

Randomized participant assignment. Randomization will occur at the church cluster level, with 1:1 assignment of churches to each arm. In churches with more than one group (i.e., churches with more than 20 participants, necessitating more than one group within those churches), all groups within an individual church will be randomized to the same arm. Community location based participant groups will be treated the same as if they were a church based group in the randomization process. Randomization will be conducted by a biostatistician or designated investigator, who will have no interactions with potential participants and has no supervisory role with study staff responsible for recruiting, consent, and intervention process.

Churches and community based participant groups will be blocked (i.e., grouped into similar units) according to geographic region and approximate number of adult church members. Using

a computer generated algorithm for random assignment, equal numbers of churches within each block will be assigned to the WORD DPP-LI arm and the PILI DPP-LI arm of the study.

Recruitment and Consent

Participants will be recruited through churches from Arkansas, Kansas, Missouri, and Oklahoma. The recruitment will also occur through clinics serving the Marshallese community and through local media targeting the Marshallese community. The recruitment goal is up to 400 participants through the duration of the study.

During recruitment, Marshallese study staff will give presentations and distribute study information in English and Marshallese within local community churches and meeting places. Those who express interest will complete an eligibility screener, to determine eligibility– see Inclusion/Exclusion criteria. The eligibility screener will include systolic and diastolic blood pressure and height and weight measurements to calculate BMI.

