Power, sample size, and detectable effects. All of the power calculations were conducted with PASS12.³¹ The primary objective of the analysis is to estimate the effect of the PILI DPP-LI relative to the effect of the WORD DPP-LI with respect to the percentage of weight loss from pre- to post-intervention. Based on prior PILI DPP-LI research,²¹ it is hypothesized that the adapted intervention will result in 2.5kg weight loss (SD=7) larger than the WORD DPP-LI (this is ~4% body weight loss), which reflects a medium effect size of 0.36.³² Using the randomized clustered design, it is estimated that a sample size of 32 churches (16 clusters per arm with 12 individuals per cluster) would total N=384. This achieves 91% power to detect a difference of 2.5kg between the group means when the standard deviation is 7 (ES=0.35) and the intra-cluster correlation is 0.01 using a two-sided *t*-test with a significance level of 0.05, or 80% to detect smaller effects (ES=0.31) if observed. It is planned to impute missing data (see below), therefore all randomized participants will be included in the analysis according to an intention-to-treat protocol.

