Statistical analysis plan. All of the analyses will be performed with SAS/STATv14.1. Data will be examined for distributional normality and outliers prior to any analyses. Descriptive statistics will be generated for all variables of interest included in the analysis, overall, and by intervention assignment. Univariate comparisons will consist of *t*-tests and ANOVA, and of chi-square and other non-parametric tests, if needed, for continuous and categorical variables, respectively. Randomization validity will be assessed by comparing intervention arms on baseline measures using *t*-test, chi-square test, ANOVA, and other appropriate tests. If imbalances are found, adjusting the between-group analyses for potential confounders will be considered. Primary analyses will be intention-to-treat, without regard to intervention adherence. Multivariable linear ANCOVA regression models will be used for continuous outcomes accounting for clustering effect within groups, to model and compare the PILI DPP-LI to the WORD DPP-LI (Aim 1). Using these models, treatment effects will be estimated and tested by comparing change in group-specific means at the post-intervention assessment, conservatively adjusting for baseline differences (which should be minimal by virtue of randomization) and taking in account intracluster correlation by assuming compound symmetry covariance structure.

The hypothesis is that participants randomized to the PILI DPP-LI will show a significantly higher percentage of weight loss compared to those randomized to the WORD DPP-LI. The main independent variable of interest is intervention assignment (PILI DPP-LI vs. WORD DPP-LI) and the primary outcome is percent body weight loss from pre- to post-intervention

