perform multiple imputations (N=25) in SAS PROC MI when assuming observations are missing at random (MAR); and 3) perform pattern-mixture model imputations in SAS PROC MI when assuming observations are missing not at random (MNAR). To address this potential source of inferential error, we will use monotone regression-based, multiple random imputations of the outcomes. These imputations will help minimize loss of power resulting from attrition. We will use demographic covariates and prior weight measurements that are available in this predictive model. The analysis will then be carried out in multiple data sets, and the results combined using standard methods in SAS PROC MIANALYZE to produce summary effect and standard error estimates that incorporate the imputation error.³³⁻³⁴

Plans to address heterogeneity of treatment effect. Potential differential effects of the PILI DPP-LI among subgroups will be evaluated to determine its effectiveness in specific population segments. This will be done by testing two-way interactions between intervention assignment and covariates of interest. These include sex, age, education, insurance status, and marital status. Bonferroni correction will be applied to control p-values for multiple comparisons. For these exploratory comparisons, we will report all relevant subgroup outcomes analyzed.

Ethical Considerations. This study will be conducted in accordance with all applicable government regulations and University of Arkansas for Medical Sciences research policies and procedures. This protocol and any amendments will be submitted and approved by the UAMS Institutional Review Board (IRB) to conduct the study.

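### The imputation model names no church term (and no arm), so it does not match the church-randomised analysis; the error in the standard error is negligible at the plan's ICC and conditional above it

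*Combined protocol and SAP*

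**What the plan says.** All references are to the combined protocol and SAP.

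- **Design** (Randomized participant assignment): "Randomization will occur at the church cluster level, with 1:1 assignment of churches to each arm". Community groups are treated in the same way.
- **Analysis model** (Statistical analysis plan): ANCOVA and mixed models, "taking in account intracluster correlation by assuming compound symmetry covariance structure".
- **Role of imputation** (Power, sample size, and detectable effects): "It is planned to impute missing data (see below), therefore all randomized participants will be included in the analysis", under intention to treat.
- **Imputation method** (Plans to address missing data): "we will use monotone regression-based, multiple random imputations of the outcomes". The predictors named are demographics and earlier weight readings, with 25 imputations in PROC MI. Neither church nor intervention arm is named.
- **Alternatives** (same section): three approaches are to be compared: a random-effects model on all available data, labelled as assuming MCAR; multiple imputation under MAR; and pattern-mixture imputation under MNAR. None is named as primary, and no expected missing rate is given.

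**The concern.** An imputation model should contain the structure that the analysis model will estimate. Here the analysis model has a church component, and the imputation model as described has none. A missing participant's weight would be drawn from a trial-wide regression, without reference to how the rest of that church did. Imputed members are then uncorrelated with their church, apart from whatever their own demographics and earlier weights carry. The completed data show less clustering than the real data, and the compound-symmetry model reads the diluted value. Rubin's rules add imputation variance but do not put back the lost between-church variance.

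At stake is the precision claimed for the treatment comparison, if the imputed analysis is the one reported. Approach 3 also runs through PROC MI and may share the problem.

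**Working it through.** **Inputs from the documents.** "32 churches (16 clusters per arm with 12 individuals per cluster) would total N=384", so m = 12 and 192 per arm. Difference 2.5 kg, SD 7 kg, two-sided alpha 0.05, ICC 0.01, and 25 imputations.

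**Assumed, because the documents give no figure.** Missing fraction f (mainly 20-30%; 10-40% as the outer range) and ICC values (rho) above 0.01.

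**The plan's own figure.** Design effect = 1 + 11 × 0.01 = 1.11. Effective n per arm = 192/1.11 = 173.0. SE = 7 × √(2/173.0) = 0.753, and 2.5/0.753 = 3.32. Power = Φ(3.32 − 1.96) = 91.3%. The stated 91% reproduces (89.5% with a t-test on 30 df).

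**Step 1: dilution.** Two members of a church keep their correlation only if both are observed, so the completed-data ICC is about rho × (1 − f)². At 20% missing, 0.01 becomes 0.01 × 0.64 = 0.0064. At 30% missing, 0.05 becomes 0.05 × 0.49 = 0.0245. Simulation agreed: at 20% missing, 0.0059 for a true 0.01 and 0.031 for a true 0.05 (formula 0.032).

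**Step 2: pooled SE with arm in the imputation model.** The variance of an arm mean, scaled by n/SD², with outcomes missing completely at random and no predictive gain from covariates, is:

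- true: m·rho + (1 − rho)/(1 − f)
- as pooled: m(1 − f)²·rho + (1 − f)(1 − rho) + f + (1 + 1/25)·[f + f²/(1 − f)]

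Example, rho = 0.05 and f = 0.2. True = 0.6 + 0.95/0.8 = 1.7875. Pooled = 0.384 + 0.760 + 0.200 + 1.04 × 0.25 = 1.6040. SE ratio = √(1.6040/1.7875) = 0.947.

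| ICC | Missing | Completed ICC | True | Pooled | SE ratio |
|---|---|---|---|---|---|
| 0.01 | 20% | 0.0064 | 1.3575 | 1.3288 | 0.989 |
| 0.01 | 30% | 0.0049 | 1.5343 | 1.4975 | 0.988 |
| 0.03 | 20% | 0.0192 | 1.5725 | 1.4664 | 0.966 |
| 0.03 | 30% | 0.0147 | 1.7457 | 1.6011 | 0.958 |
| 0.05 | 20% | 0.0320 | 1.7875 | 1.6040 | 0.947 |
| 0.05 | 30% | 0.0245 | 1.9571 | 1.7047 | 0.933 |

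**Step 3: simulation with arm in the imputation model.** 32 churches of 12, outcomes missing completely at random, 2,500 to 4,000 trials per cell where counted; Monte Carlo error on the ratio is about 1.4% at 2,500 trials.

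- ICC 0.01: ratio of reported SE to true SD 0.97-1.02; type I error 4.4-4.8%.
- ICC 0.03-0.05, 20-30% missing: ratio 0.91-0.96; type I error 4.8-6.6%, depending partly on the degrees of freedom used.
- ICC 0.10, as an outer case: ratio 0.86-0.91 at 20-40% missing; type I error 7.9% at 30% missing.

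Some of the lowest figures are partly noise. In the set that gave 0.91 at ICC 0.05 with 20% missing, the complete data gave 0.881/0.920 = 0.96.

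**Step 4: predictors exactly as listed, without arm.** For the post-intervention weight, the earlier weight is the baseline one, which randomisation makes unrelated to arm, so it cannot stand in for arm. The effect shrinks to about 2.5 × 0.8 = 2.0 kg at 20% missing and 2.5 × 0.6 = 1.5 kg at 40%. Simulation gave 2.00-2.02 and 1.49-1.51. The SE ratio was 1.12-1.52. In null simulations (ICC 0.01-0.05, 10-30% missing) type I error was 0.5-3.6%.

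**Step 5: church random intercept plus arm.** Completed-data ICC was 0.049 for a true 0.05 (20% missing) and 0.097 for a true 0.10 (40% missing). SE ratios were 0.97 and 0.99, with coverage of about 95% in both. At ICC 0.01 with 20% missing the ratio was 1.03-1.05, slightly conservative.

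**The case against.** Four points weigh against the concern.

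1. **The direction depends on arm.** A reader might infer that the plan's confidence interval is too narrow and its false-positive rate above 5%. The documents do not support that. If the predictor list is complete enough to show that church is absent, it equally shows that arm is absent, and then the standard error is too large rather than too small. This stands: the narrow-interval result needs arm to be in the model.
2. **The planned ICC is 0.01**, where nothing material happens. This also stands. However, the power section gives no source for 0.01. Sessions are delivered in groups by lay educators, which could create within-church correlation. Churches with more than 20 participants are foreseen, and larger clusters make dilution matter more. The method should stay valid if the observed ICC is higher.
3. **Silence is not exclusion.** The text does not call its list exhaustive, and church could be added as a class effect. This stands in part. A specific method and predictor set are given, and the fair reading is a single-level regression.
4. **A safeguard exists.** The random-effects model on all available data needs no imputation. This stands in part. It is one of three approaches in a sensitivity check, none is named primary, and the power section points to imputation. If the results differ, the plan does not say which governs.

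**Conclusion.** The mismatch is real: church is in the design and the analysis model but not among the named imputation terms. Its consequence is conditional.

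- **With arm included:** the SE is about 1-2% too small at the plan's ICC of 0.01, with no type I inflation. It is about 3-9% too small at ICCs of 0.03-0.05 with 20-30% missing, with type I error of roughly 5-6.6%.
- **With the list taken literally:** the omission of arm dominates. The estimate is attenuated by about the missing fraction, and the SE is not too small.

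Adding arm alone would cure the larger problem and expose this one, so the two belong in one correction. The sizes rest on assumed missing rates, assumed ICCs above 0.01, data missing completely at random, and an analysis not adjusted for baseline. Whether the imputed result would be the primary one is itself an inference, because the plan does not say.

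**What to change.** - Name approach 1, with church or community site as the clustering term, as the primary analysis on all observed weights. Correct its label: a likelihood-based mixed model is valid under missing at random and does not need MCAR.
- Run the imputation analyses as sensitivity. Use a multilevel imputation model with a church or site random intercept and intervention arm, alongside the demographics and earlier weights. Apply the same structure to the pattern-mixture imputations.
- Reword the sentence in the power section that makes imputation the reason all randomised participants are analysed, so that it agrees with the chosen primary analysis.

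**Cost:** SAP wording and a different imputation routine; no new data. Intervals will be slightly wider if the true ICC exceeds 0.01.

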Sensitivity analyses to determine the impact of key assumptions. We will examine the distributional assumptions for our outcome measures, which may prompt transformations if justified. We will also compare the results of parametric and non-parametric univariate tests (for instance Wilcoxon test, Kolmogorov-Smirnov test, or Fisher's Exact test, respectively) as a sensitivity step to confirm the inferences. In a case where distributional assumptions are not met, non-parametric tests will be applied. While we will track and analyze the effect of dosage (number of sessions completed), we will use an intention-to-treat analysis. To account for missing data we will compare imputation methods under several assumed missing data mechanisms, missing completely at random (MCAR), missing at random (MAR), and missing not at random (MNAR), in order to determine which underlying mechanism best fits our data.

Plans to address missing data. The study team will minimize missing data by using highly qualified staff to systematically collect data from all participants. Furthermore, we will use REDCap to monitor the occurrence of missing data during field collection. REDCap has a standard missing data report to facilitate the identification of missing data fields, which allows for continuous data quality monitoring so that missing data can be immediately collected. If a participant drops out, the study team will document why the drop out occurred. The study team will continue to collect information on all outcomes from participants, unless consent is withdrawn. Given recent advances in handling missing data in longitudinal studies, we have several reasonable approaches that we will apply and compare. We will compare the results of the analysis using three approaches as a comprehensive sensitivity check: 1) use a random effects model in SAS PROC MIXED (or weighted GEE for discrete outcomes) that makes use of all available data when assuming observations are missing completely at random (MCAR); 2)

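### The imputation model does not name randomised arm; followed as written, it shrinks the post-intervention PILI–WORD difference by about the fraction of weights missing

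*Combined protocol and SAP*

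**What the plan says.** Plans to address missing data sets out three approaches to be compared:

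- a mixed model: "use a random effects model in SAS PROC MIXED (or weighted GEE for discrete outcomes) that makes use of all available data";
- 25 multiple imputations in PROC MI assuming missing at random (MAR);
- pattern-mixture imputations in PROC MI assuming missing not at random.

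On how values are imputed, it says "we will use monotone regression-based, multiple random imputations of the outcomes". The predictors are then given in one sentence: "We will use demographic covariates and prior weight measurements that are available in this predictive model". No other sentence in the document lists imputation predictors. Arm is neither named nor expressly excluded, and imputation by arm is not mentioned.

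Three other places bear on this:

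- Statistical analysis plan makes intervention assignment the main independent variable of the outcome model.
- Power, sample size, and detectable effects ties the intention-to-treat analysis to imputation: "It is planned to impute missing data (see below), therefore all randomized participants will be included in the analysis".
- Sensitivity analyses to determine the impact of key assumptions says the imputation methods will be compared "in order to determine which underlying mechanism best fits our data".

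**The concern.** An imputation model should contain every variable in the analysis model, above all the one being tested. Here the only weights available before the post-intervention assessment are those taken at screening and at the pre-intervention event. Both precede the intervention, so neither carries any of its effect, and randomisation should balance them and the demographic covariates. An imputed post-intervention weight therefore has the same expected value in either arm, given those covariates. Imputed participants dilute the contrast, whatever the reason for missingness.

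Two things are at stake. First, if the imputed analysis supports the main conclusion, a real difference between two active programmes may be understated or missed. Second, the mixed model contains arm and the imputation model does not, so the two could disagree for that reason alone. Because the plan compares methods in order to judge the missing-data mechanism, that gap could be taken as evidence about the mechanism.

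**Working it through.** **Inputs from the power section.** Difference 2.5 kg, SD 7, 16 churches per arm, 12 participants per church (192 per arm, N=384), ICC 0.01, two-sided 0.05. The missing fraction f is not given, so 10 to 40% is an assumed range. The work is in kg because the power section is; the proportional shrinkage carries over to percent weight loss.

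**1. The plan's own figure.** Design effect = 1 + (12 − 1) × 0.01 = 1.11. SE = 7 × √(2 × 1.11/192) = 0.753. 2.5/0.753 = 3.32. Normal-approximation power = Φ(3.32 − 1.96) = 0.913. A noncentral t gives 0.912 on 382 df and 0.895 on 30 cluster df. The stated 91% is reproduced.

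**2. Expected difference with arm omitted.** In each arm a fraction 1 − f is observed and carries the true difference δ. The fraction f is imputed and carries none. So E[difference] = δ(1 − f):

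- 5%: 2.5 × 0.95 = 2.375 kg
- 10%: 2.5 × 0.90 = 2.25 kg
- 20%: 2.5 × 0.80 = 2.00 kg
- 30%: 2.5 × 0.70 = 1.75 kg
- 40%: 2.5 × 0.60 = 1.50 kg

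If missingness differs by arm, the factor is 1 − [f₁(1 − f₀) + f₀(1 − f₁)]/(2 − f₁ − f₀). For 30% and 10% this is 1 − (0.27 + 0.07)/1.6 = 0.7875; simulation gave 0.789.

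**3. Simulation.** Outcomes missing completely at random, 25 regression imputations pooled by Rubin's rules, church-mean t-test on 30 df, 8,000 replicates per setting (Monte Carlo error about 0.5 points of power). With nothing missing, power is 89.6% (20,000 replicates).

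| Missing | Arm omitted: kg | power | Arm included: kg | power | Available data, arm in model: kg | power |
|---|---|---|---|---|---|---|
| 10% | 2.246 | 81.4% | 2.496 | 87.0% | 2.495 | 86.4% |
| 20% | 2.007 | 68.9% | 2.511 | 83.4% | 2.510 | 82.6% |
| 30% | 1.758 | 52.1% | 2.515 | 79.3% | 2.514 | 78.8% |
| 40% | 1.497 | 31.6% | 2.499 | 71.9% | 2.498 | 72.0% |

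The arm-included column shows the loss from attrition alone. The omission itself costs 5.6, 14.5, 27.2 and 40.3 points of power. The last two columns use weighted church means as an analogue of the planned mixed model.

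A second simulation used individual-level ANCOVA with cluster-robust standard errors (600 trials per setting; assumed baseline weight mean 90 kg, SD 18, and WORD loss 2 kg). At 10, 20 and 30% missing it gave 2.21, 2.06 and 1.75 kg with arm omitted, and 2.45, 2.58 and 2.51 kg with arm included (Monte Carlo SE about 0.03).

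**4. Why power falls so far.** At 30% missing with arm omitted, the mean reported SE is 0.84 against an empirical 0.63. The estimate shrinks but its standard error does not.

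**5. Twelve months.** If the post-intervention weight is observed, it passes on part of the arm effect. Assume 2.5 kg at both times and within-arm correlation ρ between the two weight changes. The slope fitted without arm is (49ρ + 2.5²/4)/(49 + 2.5²/4), which is 0.515, 0.709 and 0.903 for ρ = 0.5, 0.7 and 0.9. At 30% missing, 2.5 × (0.7 + 0.3 × slope) gives 2.14, 2.28 and 2.43 kg. Simulation with 1,000 replicates gave 2.10, 2.26 and 2.42 kg.

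**The case against.** The strongest reply is that the predictor sentence does not claim to be complete. It could be read as naming auxiliary variables, with arm taken for granted. That stands as a limit: the bias follows only if the sentence is programmed as it reads. But it is the plan's only specification, and leaving the choice until results are visible would let it move the estimate.

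Second, the primary analysis may escape. Statistical analysis plan describes the approach for the primary outcome as a general linear mixed model, and the three missing-data approaches are presented as a sensitivity check. The mixed model on available data is indeed unaffected. Against that, the power section makes imputation the reason all randomised participants can be analysed, and the missing-data section relies on it to limit the loss of power. The plan is ambiguous on which analysis leads.

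Third, the large losses need high attrition. At 5% missing, power was 86% without arm and 88% with it (1,500 replicates). The plan also provides wide collection windows, re-contact for missing data and continued follow-up after dropout. This is fair: the size of the problem depends on the attrition that occurs.

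Fourth, the error is one-directional under equal random missingness. With no true difference, rejection without arm was 2.5% at 10% missing and 0.4% at 30%, against a nominal 5%. It does not create a false PILI advantage. In a comparison of two active programmes, a spurious finding of no difference is still an error that matters.

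Finally, all simulations used data missing completely at random and ordinary regression imputation. The pattern-mixture model is not specified, so the size of any effect there is unknown.

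**Conclusion.** The concern holds. Followed as written, the imputation rule biases the post-intervention difference toward zero by about the fraction missing: 10% of the effect at 10% missing and 30% at 30%. On the plan's design inputs, the omission costs about 6 points of power at 10% missing and 27 at 30%, beyond what attrition costs. The shrinkage factor for equal missingness does not depend on SD, ICC or outcome scale. The power figures rest on the plan's SD of 7 and ICC of 0.01, an assumed missing fraction and data missing completely at random. The mixed model on available data is not affected, and the 12-month shrinkage is smaller where the post-intervention weight is observed. This should be corrected before the analysis is programmed.

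**What to change.** Replace the predictor sentence with:

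> For both the MAR and the pattern-mixture imputations, weights will be imputed separately by randomised arm, or with arm as a predictor, alongside baseline weight, other prior weights and demographic covariates.

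Keep the 25 imputations and the pooling in PROC MIANALYZE. Optionally, where the missing pattern is not monotone, also use other observed weights, including the 12-month weight.

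The cost is one sentence in the plan and one variable or BY statement in the code, with no new data. At the planned ICC of 0.01, adding arm alone has no material downside: at 30% missing the mean SE was 0.87 against an empirical 0.89.

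Church is not needed to remove this bias, but that reassurance on standard errors does not extend to larger ICCs. With arm included and church omitted at 30% missing, the mean SE was 0.93 against an empirical 1.01 at ICC 0.05, and 1.00 against 1.14 at ICC 0.10, with null rejection of 6.5% and 7.2%. If church is added, it should enter as a random effect through multilevel imputation. Fixed church indicators inflate the standard error (1.15 against an empirical 0.91 at 30% missing) and give 59% power, against 79% with arm alone.

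### The imputation model leaves out attendance, which the trial records, so weight loss can be overstated and the PILI–WORD difference biased in either direction

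*Combined protocol and SAP*

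**What the plan says.** All of this stands in the Data Analysis section of the combined protocol and SAP.

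- *Power, sample size, and detectable effects*: "It is planned to impute missing data (see below), therefore all randomized participants will be included in the analysis". Imputation therefore carries the intention-to-treat population. No attrition allowance is stated.
- *Statistical analysis plan*: the primary outcome is percent weight loss from before to after the intervention, and the primary analysis ignores adherence.
- *Plans to address missing data*: three approaches are to be compared. These are a random-effects model on available data (labelled MCAR), 25 multiple imputations (MAR) and pattern-mixture imputation (MNAR). None is named as the leading one. The predictors are given in one sentence: "We will use demographic covariates and prior weight measurements that are available in this predictive model". Arm, church and attendance are not among them. The pattern-mixture analysis has no stated patterns, shifts or reference group.
- *Sensitivity analyses*: "While we will track and analyze the effect of dosage (number of sessions completed), we will use an intention-to-treat analysis".
- *Plans to address missing data*, on drop-outs: "If a participant drops out, the study team will document why the drop out occurred", and "The study team will continue to collect information on all outcomes from participants, unless consent is withdrawn". So some people who stop the programme should still be weighed.

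Neither attendance nor drop-out reason is linked to the imputation.

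**The concern.** Imputation under MAR is credible only if the variables that drive both missingness and outcome are in the model. In a 24-week group programme, ceasing to attend is a leading candidate: it may plausibly make a person harder to weigh and reduce the weight lost. The listed predictors cannot carry that information for the primary outcome, because they are all fixed at baseline.

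If stopping matters in this way, an unweighed stopper is imputed like the average weighed person with similar baseline values, and most of those are attenders. Weighed stoppers are in the pool but diluted, although they are the people best placed to represent unweighed stoppers. The estimate then drifts from its target, the effect in everyone randomised whether or not they attended.

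The schedules also differ. WORD has 16 modules, 8 weekly then 8 fortnightly; PILI has 14, 4 weekly then 10 fortnightly. Stopping may therefore differ by arm, and cancellation cannot be assumed.

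**Working it through.** **The plan's own figure.** The plan gives no figure for missing data. Its power statement reproduces: design effect 1 + 11 × 0.01 = 1.11, effective size 192/1.11 = 173.0 per arm, power 0.913 against the stated 91%. That does not test this point.

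**Inputs.** From the documents: a planned difference of 2.5 kg and 192 people per arm. Assumed, because no rates are given: attenders lose 4.5 kg (PILI) or 2.0 kg (WORD), a gap of 2.5 kg; stoppers lose 0; 25% stop in each arm; weight is missing in 5–10% of attenders and 50–80% of stoppers; baseline variables do not predict stopping. The illustration is in kg because the planning figures are.

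**Formulas.** Let s be the share stopping, L and S the mean loss in attenders and stoppers, and a and b the share missing in attenders and stoppers.

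- True arm mean = (1−s)L + sS.
- Weighed mean = [(1−s)(1−a)L + s(1−b)S] / [(1−s)(1−a) + s(1−b)].
- Arm in the model: missing people receive their own arm's weighed mean, so the imputed arm mean equals the weighed mean.
- Predictors as listed: missing people receive the weighed mean of both arms pooled. With m = (1−s)a + sb, the imputed arm mean = (1−m) × weighed mean + m × pooled mean.

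**Equal stopping, 25%.** Truth: 0.75 × 4.5 − 0.75 × 2.0 = 3.375 − 1.500 = 1.875 kg.

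- a = 5%, b = 50%, arm in model: 2.5 × 0.7125/0.8375 = 2.13 kg. As listed: PILI 3.656, WORD 1.874, difference 1.78 kg.
- a = 10%, b = 60%, arm in model: 2.5 × 0.675/0.775 = 2.18 kg. As listed: 1.69 kg.
- a = 10%, b = 80%, arm in model: 2.5 × 0.675/0.725 = 2.33 kg. As listed: PILI 3.870, WORD 2.182, difference 1.69 kg.

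The other two corners of the assumed range give 2.5 × 0.675/0.800 = 2.11 and 2.5 × 0.7125/0.7625 = 2.34 kg with arm in the model. As listed, the difference reduces to 2.5 × 0.75 × (1−a), which is 1.69–1.78 kg throughout.

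Mean loss over both arms is truly (3.375 + 1.500)/2 = 2.44 kg. At the first and third settings it is imputed as 2.76 and 3.03 kg under either model, which is 0.33 and 0.59 kg too high.

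**Unequal stopping, same loss assumptions (first and third settings).**

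| Stopping PILI / WORD | True | Arm in model | As listed |
|---|---|---|---|
| 30% / 20% | 1.55 | 1.90–2.21 | 1.59–1.60 |
| 20% / 30% | 2.20 | 2.35–2.44 | 1.76–1.96 |

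**Other assumptions.** Weight is missing in 70% of stoppers and 5% of attenders unless stated. Attenders lose 1.5 kg (WORD) or 4.0 kg (PILI), and stoppers lose 0, unless stated.

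| Scenario | True | Arm in model | As listed |
|---|---|---|---|
| 30% stop in each arm | 1.75 | 2.20 | 1.66 |
| Same, 20% missing in everyone | 1.75 | 1.75 | 1.40 |
| PILI 40%, WORD 20% stop | 1.20 | 1.91 | 1.43 |
| PILI 20%, WORD 40% stop | 2.30 | 2.47 | 1.85 |
| PILI 15%, WORD 45% stop; attenders lose 4.0 and 2.5 | 2.02 | 1.80 | 1.34 |
| PILI 20%, WORD 40% stop; attenders lose 2.5 in both | 0.50 | 0.25 | 0.19 |
| 30% stop in each arm; stoppers lose 1.5 less than attenders of their arm | 2.50 | 2.50 | 1.89 |

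**Does attendance repair it?** In a simulation of the first scenario (1,500 trials, 384 people, 32 clusters, 25 imputations), the model with arm but no stopping status gave a difference of 2.22 kg and a mean loss of 2.42 kg, against true values of 1.75 and 1.93. Adding stopping status by arm gave 1.77 and 1.93. In the three simulated scenarios with unequal stopping (40/20 each way, and 45/15) the repaired differences were 1.21, 2.30 and 2.01 kg, against 1.20, 2.30 and 2.02. By construction, unweighed stoppers there resemble weighed stoppers of the same arm.

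**The case against.** The strongest defence is that the plan does not rely on one imputation. It compares three approaches, one of them MNAR, and does not call the MAR imputation primary. It also follows people after drop-out, and the more stoppers are weighed, the smaller the bias. This stands in part, but it does not close the gap. Attendance has no stated role in the random-effects analysis. In this illustration, comparing the available data by arm gives the same means as imputing with arm in the model, so it shares that bias. The pattern-mixture analysis could address stopping, but its patterns are undefined.

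For the 12-month outcome, a measured post-intervention weight is a listed predictor, so the gap is narrower there for people who have one.

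Three stronger readings are tempting, and the documents support none of them.

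- A reader might infer that the omission usually inflates the PILI–WORD difference. Both programmes are active, so the bias is PILI's minus WORD's. With arm in the model it was up, nil or down. With the predictors as listed the difference was too small in most scenarios.
- A reader might infer that unweighed stoppers are imputed as if they had kept attending. They are imputed from all weighed people, including weighed stoppers.
- A reader might infer that MAR certainly fails. It fails only if stopping predicts both missingness and outcome given the listed predictors, which is plausible but not shown.

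The repair has limits. With 25% stopping there are 48 stoppers per arm, and with 50–80% of them unweighed only about 10–24 inform the imputation. Stopped attending is not defined in the plan, and makeup sessions blur it. Drop-out reason exists only for those who dropped out, so it is a weak general predictor.

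**Conclusion.** The concern holds as a correctable weakness in the stated imputation model. Sessions completed are recorded, bear on the most plausible route to informative missingness, and are not among the predictors.

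If stoppers lose less and are more often unweighed, mean loss is overstated, by 0.33–0.59 kg at the settings shown for 25% stopping. With arm in the model this applies within each arm. With the predictors as listed it applied in both arms in nearly every such scenario; the exception was PILI when stoppers kept the between-arm gap (3.51 against 3.55 kg).

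The direction for the primary comparison cannot be stated. Under equal 25% stopping, a true 1.88 kg becomes 2.13–2.33 kg with arm in the model and 1.69–1.78 kg as listed. Adding arm alone would thus turn an understatement into an overstatement, so arm and attendance need to go in together.

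All rates and losses here are assumptions. If missingness is unrelated to stopping and arm is in the model, leaving out attendance does no harm.

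**What to change.** In *Plans to address missing data*:

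1. Add to the imputation model arm, the proportion of offered modules completed, and an indicator of having stopped attending. Either interact the attendance terms with arm or impute within arm. Use the proportion, not the count, because the arms offer 16 and 14 modules.
2. Define the stopping indicator in advance, for analysis purposes, and say how makeup sessions count.
3. State that these are auxiliary variables for imputation only. Attendance arises after randomisation and does not belong in the intention-to-treat analysis model.
4. Define the pattern-mixture patterns by stopped versus still attending.

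This changes SAP wording only, since sessions completed are already tracked. If attendance records are complete, it fits the planned monotone regression. The cost is wider intervals, possibly more than slightly, if few stoppers are weighed in an arm. In that case, use the proportion of modules completed as a continuous predictor.
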